4.1. Inclusion Criteria

Subjects must meet all of the following inclusion criteria to be eligible for enrollment into the study:

1. Evidence of personally signed and dated informed consent document by the legal representative and an assent document by the subject indicating that the subject and a legal representative have been informed of all pertinent aspects of the study.
2. Subjects and their legal guardians who are willing and able to comply with scheduled visits, treatment plan, laboratory tests, and other study procedures.
3. The subjects must have received investigational product in Study A1281198 and completed at least 3 weeks of double blind treatment before entering this open label extension. However, subjects who have insufficient treatment response and have reached their maximum tolerated dose may enroll in the open label extension as early as 1 week after the end of their titration.
4. In the investigator's opinion, the subject must be likely to benefit from antipsychotic therapy and must have been free from any clinically significant safety concerns during the preceding double blind study (ie, in the opinion of the investigator, the benefits that the subject is likely to derive from continued participation must outweigh the risks).
5. All fertile male subjects and female subjects of childbearing potential who are sexually active and/or their legal guardians, as appropriate, must agree that a highly effective method of contraception be used as outlined in this protocol and for the duration of the study and for 28 days after the last dose of investigational product.

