9. DATA ANALYSIS/STATISTICAL METHODS

Detailed methodology for summarization of the data collected in this trial will be documented in a Statistical Analysis Plan (SAP). The SAP may modify the plans outlined in the protocol; however, any major modifications of significant change to the primary endpoint definition and/or its analysis will also be reflected in a protocol amendment.

As this is an open label study with no comparator, no inferential statistics will be performed. Quantitative variables will be described by standard descriptive statistics (n, mean, standard deviation, minimum, and maximum, 95% confidence intervals), and qualitative variables will be summarized by frequency tables. Summaries will include data for all subjects who took at least one dose of investigational product in this open label extension study.

Baseline values for efficacy, outcomes and special safety endpoints will be the last observation made prior to the subject receiving open label treatment. For safety, for those subjects who were randomized to placebo in the double blind study, baseline values will be the last (pre dose, for ECG and blood pressure/pulse only) observation prior to initiating dosing in the open label extension study normally, the (pre dose, for ECG and blood pressure/pulse only) observation of the last visit in the double-blind study; and for those subjects who were randomized to ziprasidone in the double blind study, baseline values will be the last observation prior to initiating dosing in the double blind study (normally, the value from the Baseline visit in the double blind study).

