9.3. Safety Analysis

The safety assessments include:

- Adverse event reporting, [including Possibly Suicide Related Adverse Events (PSRAEs)];
- Clinical laboratory values;
- Physical Exams;
- Vital signs (blood pressure, pulse rate);
- Weight, height, BMI, BMI Z-score, waist circumference;
- Electrocardiograms;
- No formal statistical analysis will be conducted on any of the above safety data.

Data for height, weight, BMI, and waist circumference will be summarized by time point using descriptive statistics. Additionally, height, weight, and BMI will be standardized using CDC (Child Development Chart) growth charts and the resulting z scores presented in

listings and frequency tables in 1 unit intervals. In addition, frequency tables of above/below a 1 point increase in the z scores for BMI will be presented.

All randomized subjects who receive at least one dose of antipsychotic treatment will be included in the safety data summarization. All adverse events that are observed from the time of first dosing with open label investigational product until the end of study participation will be included in data summaries.

All adverse events will be coded according to the Medical Dictionary for Regulatory Activities. The incidence of treatment emergent adverse events will be tabulated by system organ class. The incidence of treatment emergent adverse events will be displayed by severity and attribution. In addition, the incidence of serious adverse events and adverse events that cause withdrawal will be tabulated. All adverse events will be listed.

All clinical laboratory data will be displayed in listings grouped by type of laboratory test (eg, hematology, blood chemistry) for each sample collection date. Values outside of the normal range will be noted; the respective normal high or low value will be presented in parentheses, linked to the abnormal laboratory value. Laboratory values will be summarized as median changes from baseline and also by frequency of occurrence of clinically significant abnormal values.

All vital sign measurements will be displayed in listings by subject for each sample collection date and time.

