3.4. Baseline Variables

No baseline covariates in the planned analysis.

Baseline visit for the open-label extension study will be the final visit of the double blind trial (Week 4 or early termination visit from A1281198), except for safety ECG parameters. For ECG parameters, baseline values will be the value from the Baseline visit in the double-blind study A1281198.

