4. ANALYSIS SETS (POPULATIONS FOR ANALYSIS)

4.1. Safety Analysis Set

As the objective of the study is long-term safety and tolerability of ziprasidone, only one analysis set, “Safety Analysis Set” defined below will be used for data summaries.

The Safety Analysis Set (SAS) will include *all subjects who took at least one dose of study medication in this open-label extension study.*

All summaries will be based on the “as reported” visits (as recorded on the Case Report Forms).

For data summary purposes, subjects will be classified into one of the following two groups:

- Ziprasidone/Ziprasidone: randomized to ziprasidone in the preceding double-blind study (and on ziprasidone in the current open-label extension study).
- Placebo/Ziprasidone: randomized to placebo in the preceding double-blind study (and on ziprasidone in the current open-label extension study).

In addition, the above two groups will be combined as:

- Combined: combination of the two groups Ziprasidone/Ziprasidone and Placebo/Ziprasidone. This is essentially the set of all subjects in the current open-label extension study.

Data summaries will be done based on Ziprasidone/Ziprasidone and Placebo/Ziprasidone, as well as Combined.

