6.5.1. Adverse Events

All randomized subjects who receive at least one dose of antipsychotic treatment will be included in the safety data summarization. All treatment emergent adverse events that are observed from the time of first dosing with open label investigational product until the end of study participation will be included in data summaries. All causality discontinuations and treatment emergent discontinuations from the study will be summarized.

An adverse event is considered treatment emergent relative to a given treatment if:

- the event occurs for the first time during the time of first dosing with open label investigational product until the end of study participation and was not seen prior to the start of treatment in open-label extension (for example, during the baseline or double-blind study), or

- the event was seen prior to the start of treatment but increased in severity during treatment.

All adverse events will be coded according to the Medical Dictionary for Regulatory Activities. The incidence of treatment emergent adverse events will be tabulated by system organ class. The incidence of treatment emergent adverse events will be displayed by severity and attribution. In addition, the incidence of serious adverse events and adverse events that cause withdrawal will be tabulated. All adverse events will be listed.

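### Non-serious adverse events that began on double-blind ziprasidone and persist or recur unchanged in the extension are listed but enter no specified incidence table

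*SAP*

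**What the plan says.** Protocol 9.3 states that all adverse events observed from first open-label dosing to the end of participation will be in the data summaries. That sentence has no treatment-emergent restriction. The section then prescribes the tables: "The incidence of treatment emergent adverse events will be tabulated by system organ class", with displays by severity and attribution. The protocol does not define treatment emergent.

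SAP 6.5.1 keeps the same window ("from the time of first dosing with open label investigational product until the end of study participation") but limits the summaries to treatment-emergent events. Its definition opens "An adverse event is considered treatment emergent relative to a given treatment if" and has two limbs. Either the event occurs for the first time in the extension and "was not seen prior to the start of treatment in open-label extension (for example, during the baseline or double-blind study"), or it was seen earlier and increased in severity. All events are listed. Serious events and events causing withdrawal are tabulated, without being limited to treatment-emergent ones.

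SAP 4.1 reports three columns: Ziprasidone/Ziprasidone ("randomized to ziprasidone in the preceding double-blind study (and on ziprasidone in the current open-label extension study")), Placebo/Ziprasidone, and Combined. The emergence rule is the same for all of them.

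**The concern.** The study's only objective is long-term safety and tolerability of ziprasidone, and adverse event reporting heads its primary endpoints (protocol section 2). For subjects who took ziprasidone in A1281198, time on drug begins in that study. The SAP rule nevertheless treats that time as prior. An event that ziprasidone may have brought on in the double-blind study, and that the subject still has in the extension, counts only if it worsens.

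A persisting non-serious event is a tolerability outcome. If it is missing from the incidence tables, they do not show how many subjects had the event while taking ziprasidone in the extension. The two groups are also counted from different points in their exposure, and Combined pools them.

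**Working it through.** The documents give no adverse event rates and no figure to reproduce. The check is to apply the rule to each event pattern and then see which other outputs would catch what is left out.

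**Step 1. Apply both limbs of SAP 6.5.1 to a Ziprasidone/Ziprasidone subject.**

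| Event pattern | First limb | Second limb | In treatment-emergent tables? |
|---|---|---|---|
| Began in A1281198, continues at same severity | fails (seen before) | fails (no increase) | No |
| Began in A1281198, resolved, recurs at same or lower severity | fails | fails | No |
| Began in A1281198, worsens in extension | fails | met | Yes |
| First seen in extension | met | not needed | Yes |

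The phrase about a given treatment in the lead-in does not rescue the first two rows, because the first limb names the double-blind study as a prior period.

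**Step 2. Compare the groups.** Suppose an event starts two weeks after a subject's first ziprasidone dose and then continues unchanged for months. In Placebo/Ziprasidone that first dose falls in A1281201, so the event is counted unless it was already seen earlier. In Ziprasidone/Ziprasidone the onset falls in A1281198, so the event is prior and is not counted, although it is present in the extension. The on-drug time treated as prior is:

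- Ziprasidone/Ziprasidone: normally at least 3 weeks, since protocol inclusion criterion 3 requires subjects to have "completed at least 3 weeks of double blind treatment before entering this open label extension", and up to the 4-week double-blind course. It can be shorter only for those allowed in early after insufficient response.
- Placebo/Ziprasidone: 0 weeks.

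**Step 3. See what else would catch the omitted events.** Serious events and those causing withdrawal have their own tables. Laboratory changes, weight and BMI, ECG intervals, and the movement, depression and suicidality scales are summarized separately (SAP 6.4, 6.5.2, 6.5.4, 6.5.6). What remains is the non-serious event without withdrawal, such as a symptom that no scale or test measures. Protocol 7.3.2 supplies a further case. A movement disorder is recorded as an adverse event when treatment for it is reinstated. If it was already seen at the same severity on double-blind ziprasidone, it is recorded but not tabulated. The scale summaries do not give its incidence as an event.

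**Step 4. Weight of one omitted subject.** Change in the reported rate = 1/n.

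- Combined, if all 55 expected subjects enter (protocol 9.1): 1/55 = 1.8 percentage points.
- Ziprasidone/Ziprasidone: the split is not given. Assuming about one third, one half or two thirds of 55 (18, 27 or 37 subjects): 1/18 = 5.6, 1/27 = 3.7, 1/37 = 2.7 points.

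These are the weights of one subject in any table of that size. They say nothing about how many subjects are omitted. If no event persists or recurs unchanged, the change is 0.

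**The case against.** The best defence is that new or worsened since extension entry is a coherent count, openly stated, for a study meant to add longer-term data. The double-blind onsets occurred in a separate trial. Every event is listed, and protocol section 9 lets the SAP modify its plans. Protocol 9.3 itself asks for treatment-emergent tables, so its sentence about all events could be read as setting a time window only. Carry-over is also limited at entry. Inclusion criterion 4 requires freedom from clinically significant safety concerns in the double-blind study. Exclusion criterion 1 removes subjects withdrawn for a serious event and those with arrhythmia, conduction abnormality or confirmed QTc prolongation.

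Most of this stands, and it is why the existing table should stay. It does not close the gap. A listing gives no incidence by group, the entry criteria do not bar lesser events, and the SAP does not explain why it narrows the protocol's sentence.

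A reader might go further and infer that the SAP rule contradicts protocol section 9, where for those "randomized to ziprasidone in the double blind study, baseline values will be the last observation prior to initiating dosing in the double blind study". The documents do not support that. The rule concerns measured baseline values and reaches event onset only by analogy. SAP 3.4 sets the baseline at the final double-blind visit for everything except ECG, which agrees with the emergence rule. Its exception ("For ECG parameters, baseline values will be the value from the Baseline visit in the double-blind study A1281198") applies to both groups, so it is not a principle of looking back to before first ziprasidone.

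A reader might also infer that the open-label wording of the window drops events in the blinded transition. That is not supported either: the first limb refers to the start of treatment in the extension, and SAP 4.1 counts any dose taken there.

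**Conclusion.** The point holds as a modest gap between protocol 9.3 and SAP 6.5.1. Non-serious events that began on double-blind ziprasidone, persist or recur at the same severity and do not cause withdrawal have no specified incidence table. Where such events occur, the Ziprasidone/Ziprasidone and Combined columns understate the events present on ziprasidone, and the two groups are not compared like for like.

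It would be tempting to say that the reported rates will be materially too low. The documents do not support that: they give no event rates, no persistence rates and no group split, and the effect may be zero. The conclusion rests on a literal reading of the two limbs and on the serious-event and withdrawal tables not being limited to treatment-emergent events. The per-subject figures also assume that all 55 subjects enter and use assumed group sizes. This is a cheap improvement to the reporting and does not call the study's conduct or its listings into question.

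**What to change.** In SAP 6.5.1, keep the treatment-emergent table and label it *new or worsened since extension entry*. Add one incidence table, by group and Combined, of all adverse events present at any time from the first A1281201 dose to the end of study participation, as protocol 9.3 states. Split it into events new in the extension and events that began on double-blind ziprasidone and continued or recurred. Events that began before any ziprasidone dose need a row of their own, so that the split is complete. A footnote should say that only Ziprasidone/Ziprasidone has earlier on-drug time, so the two groups have different look-back periods.

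The cost is one label, one table and a little programming. The A1281198 event records are already needed to apply the current rule. The downside is that reported rates in the added table will be higher wherever such events exist. Optionally, state that the window starts at the first dose of investigational product in A1281201, including the blinded transition; this clarifies the wording but adds no weight to the point.

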6.5.2. Laboratory Data

All clinical laboratory data will be displayed in listings grouped by type of laboratory test (eg, hematology, blood chemistry) for each sample collection date. Values outside of the normal range will be noted; the respective normal high or low value will be presented in parentheses, linked to the abnormal laboratory value. Laboratory values will be summarized as median changes from baseline and also by frequency of occurrence of clinically significant abnormal values.

6.5.3. Physical Exam

Physical examinations are to be performed at the Baseline visit (last visit in Study A1281198) and at Week 26 (or early termination). Any significant physical examination finding should be recorded as an adverse event.

6.5.4. Body Weight and Height, BMI, Waist Circumference

Data for height, weight, BMI, and waist circumference will be summarized by time point using descriptive statistics. Additionally, height, weight, and BMI will be standardized using CDC (Child Development Chart) growth charts and the resulting z scores presented in listings and frequency tables in 1 unit intervals. In addition, frequency tables of above/below a 1 point increase in the z scores for BMI will be presented.

6.5.5. Vital Signs

All vital sign measurements will be displayed in listings by subject for each sample collection date and time.

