2. STUDY OBJECTIVES AND ENDPOINTS

Primary Objective(s):	Primary Endpoint(s):

 To assess the safety and tolerability of oral ziprasidone (20-80 mg BID) during long term, open label administration in children and adolescents with Bipolar I Disorder who participated in Study A1281198. 	
 Safety Assessments; Adverse event reporting; Clinical laboratory testing; Physical examinations; Blood pressure and pulse; Height and weight; Body Mass Index (BMI) and BMI Z score; Waist circumference; Electrocardiograms, including QTc; Special Safety Assessments; Movement Disorder Scales (SARS, BAS, and AIMS); Columbia Suicide Severity Rating Scale (C-SSRS); Child Depression Rating Scale (CDRS-R); Efficacy Assessments; Young Mania Rating Scale; Clinical Global Impression of Severity (CGI-S); Children's Global Assessment Scale (CGAS).

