7.1.4. Blood Pressure and Pulse

Blood pressure will be measured in the dominant arm (as defined by the subject, parent or legal guardian) and recorded to the nearest whole numbers. Pulse rate will be measured for at least 30 seconds. Two measurements will be obtained at each visit: once while the subject is in a sitting position and then in a standing position to assess orthostatic effects. The subject should be in the sitting position for approximately 5 minutes and in the standing position for approximately 2 minutes before the measurements are obtained.

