7.1.5. Body Weight and Height, BMI, Waist Circumference

Body weight, height, and waist circumference will be measured at the Baseline visit and at Week 6 and 26 (or early termination). All measurements should be taken with the subject wearing only light indoor clothing and without shoes. Height will be measured with a stadiometer; weight will be measured with a standard physician's scale. Investigators will calculate the subject's Body Mass Index (BMI) from height and weight. A BMI and BMI z-score calculator will be provided within the Firecrest site.

BMI z-score will be used to evaluate changes in body weight. An increase in the BMI z-score (adjusted for age) of 1 or more is to be documented as an adverse event in the subject's eCRF. All BMI calculations are to be recorded by the investigator in the source documents and eCRF.

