5.2. General Methods

As this is an open label study with no comparator, no inferential statistics will be performed. Quantitative variables will be described by standard descriptive statistics (n, mean, standard deviation, minimum, and maximum, 95% confidence intervals), and qualitative variables will be summarized by frequency tables. Summaries will include data for all subjects who took at least one dose of investigational product in this open label extension study.

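### Blood pressure, vital-sign pulse and BMI z-score have no specified mean change from baseline, and no standing-minus-sitting difference is planned

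*SAP*

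**What the plan says.** Protocol 2 lists these measures among the primary endpoints: "Blood pressure and pulse; Height and weight; Body Mass Index (BMI) and BMI Z score".

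**Vital signs.** Protocol 7.1.4 takes two readings at each visit, "once while the subject is in a sitting position and then in a standing position to assess orthostatic effects". The planned output, worded alike in SAP 6.5.5 and Protocol 9.3, is: "All vital sign measurements will be displayed in listings by subject for each sample collection date and time".

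**BMI z-score.** Protocol 7.1.5 gives its purpose, "BMI z-score will be used to evaluate changes in body weight", and an adverse event rule, "An increase in the BMI z-score (adjusted for age) of 1 or more is to be documented as an adverse event". SAP 6.5.4 has "the resulting z scores presented in listings and frequency tables in 1 unit intervals", and adds that "frequency tables of above/below a 1 point increase in the z scores for BMI will be presented".

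**General rule.** SAP 5.2, repeated in Protocol 9 and the Protocol Summary, says: "Quantitative variables will be described by standard descriptive statistics (n, mean, standard deviation, minimum, and maximum, 95% confidence intervals". It mentions neither change from baseline nor a difference between positions.

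**Where change is written out.** SAP 6.5.2 specifies median change for laboratory values. SAP 6.5.6 specifies mean change for ECG variables, including heart rate.

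**Baseline.** For safety data in subjects randomized to ziprasidone, Protocol 9 uses the last value before double-blind dosing. SAP 3.4 uses the final double-blind visit for everything except ECG.

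**The concern.** The protocol states what each measurement is for, and the outputs named for it serve that purpose weakly. Sitting and standing readings are paired to show orthostatic effects, but no output forms the difference. BMI z-score is the named measure of weight change, but its only stated change output is a split at 1 point. That is the same cut-off that already triggers an adverse event record, so the table adds little to the adverse event data. Protocol 9 defines a pre-dose baseline for blood pressure and pulse, yet no section says which summary uses it.

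The study exists to provide longer-term pediatric safety data, and SAP 6.6 plans a subgroup analysis of all safety endpoints to support a submission in China. If the outputs follow the specific sections alone, a reader of the report would have no group-level estimate of change in blood pressure or vital-sign pulse. For BMI z-score the reader would have only a count of large rises.

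**Working it through.** **1. What the general rule would and would not supply.** Suppose SAP 5.2 does yield by-visit means of blood pressure, pulse and z-score.

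- Point estimates: when the same subjects contribute, mean(standing) − mean(sitting) equals the mean of the differences. The same holds for mean(visit) − mean(baseline).
- Precision: Var(standing − sitting) = Var(standing) + Var(sitting) − 2 Cov(standing, sitting). Two separate SDs do not give the covariance, so the SD and 95% CI of the difference, or of change, cannot be recovered from the separate summaries.
- If the subjects at baseline and at a visit are not the same, even the point estimate of within-subject change is not recovered.

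**2. How coarse the 1-point table is.** The plan gives no figure to reproduce here. The documents supply only the subject numbers: about 55 entrants and about 35% dropout (Protocol 9.1), so 55 × 0.65 = 35.75, taken as 36. The plan says about 40. The mean and SD of BMI z-score change are not in the documents; the values below are assumptions, with change taken as normal.

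Expected number rising by at least 1 = n × P(Z ≥ (1 − mean)/SD). The 95% CI half-width for the mean change is t × SD/√n, with t = 2.030 at n = 36.

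For mean 0.30 and SD 0.5:
- With the shift: P(Z ≥ 1.4) = 0.0808, and 36 × 0.0808 = 2.9.
- No shift: P(Z ≥ 2.0) = 0.0228, and 36 × 0.0228 = 0.8.
- Half-width: 2.030 × 0.5/6 = 0.169, so an observed mean of 0.30 has CI 0.13 to 0.47.
- An observed 3 of 36 has exact 95% CI 1.8% to 22.5%, which covers the no-shift 2.3%. Four would be needed to exclude it (lower limit 3.1%).

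Range, n = 36. The fifth column is the smallest count whose exact 95% CI lies above the no-shift rate, treating that rate as known:

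| Assumed mean | Assumed SD | Expected ≥1, shift | Expected ≥1, no shift | Count needed | 95% CI around the mean |
|---|---|---|---|---|---|
| 0.30 | 0.3 | 0.35 | 0.02 | 1 | 0.20 to 0.40 |
| 0.30 | 0.4 | 1.4 | 0.2 | 2 | 0.17 to 0.44 |
| 0.30 | 0.5 | 2.9 | 0.8 | 4 | 0.13 to 0.47 |
| 0.30 | 0.7 | 5.7 | 2.8 | 7 | 0.06 to 0.54 |
| 0.50 | 0.7 | 8.6 | 2.8 | 7 | 0.26 to 0.74 |

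In the first four rows the expected count falls short of the count needed, while the CI around the mean excludes 0. In the last row the table also shows the shift. In the fourth row the mean is better but not decisive, since its lower limit is close to 0.

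Other n, at mean 0.30 and SD 0.5: with 40 subjects, 3.2 against 0.9 and half-width 0.16; with all 55, 4.4 against 1.25 and half-width 0.135.

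**3. Baseline.** For subjects randomized to placebo, Protocol 9 and SAP 3.4 normally point to the same visit for non-ECG data. For subjects randomized to ziprasidone they do not: under the SAP, change over the double-blind weeks (up to 4) is left out; under the protocol it is included. A change table cannot be built unambiguously until one is chosen.

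**The case against.** - **The general rule already covers this.** SAP 5.2 does not exclude vital signs, and SAP 6.5.5 does not say that listings are the sole output. This stands in part. A reader might infer that blood pressure and pulse will be listed and never summarized; the documents do not go that far. Even on the generous reading, change and the orthostatic difference are unspecified.
- **Pulse is partly covered.** SAP 6.5.6 gives mean change in ECG heart rate. This stands, but it is a supine reading (Protocol 7.2) and says nothing of blood pressure or standing pulse.
- **The BMI z-score plan is coherent.** A purpose, a threshold and a matching table are all stated, and raw BMI and weight are summarized by time point. This stands: the table is a group-level change measure, and calling it coarse is a judgement, not the discovery of a contradiction.
- **Dropout.** A reader might infer that raw means are distorted because leavers have no Week 26 value. The documents do not support that: Protocol 6.4 requires the Week 26 assessments at early termination, and Protocol 7.1.5 names early termination for weight and height. Whether those values are tabulated with Week 26 is not stated, so no size is attached to this.
- **No inference is planned.** True, but 95% confidence intervals are already among the planned descriptive statistics, and nothing more is asked for here.

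**Conclusion.** The point holds as a gap in specification. No section of either document specifies mean within-subject change in blood pressure, vital-sign pulse or BMI z-score, or any standing-minus-sitting difference, although the protocol names the purposes that these would serve.

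Its size can only be illustrated. At 36 subjects, a mean rise of 0.30 and SD 0.5, 2.9 against 0.8 subjects would cross 1 point. The mean and SD are assumptions, and with a larger shift (0.50 at SD 0.7) the table does the job too. No size is given for the orthostatic difference, since the documents state neither its SD nor the correlation between positions.

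A reader might conclude that results would be invalid or data lost. They would not: every vital-sign value is listed by subject, date and time, z-scores are listed too, and change can be derived later. This is an inexpensive improvement to a descriptive plan.

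**What to change.** - **SAP 6.5.5 and Protocol 9.3:** add change from baseline by visit (n, mean, SD, 95% CI) for sitting and standing blood pressure and pulse, and for the standing-minus-sitting difference. Keep the listings, which still show individual drops that a mean can hide.
- **SAP 6.5.4 and Protocol 9.3:** add mean change (SD, 95% CI) by time point in BMI z-score. Keep the 1-unit bins and the 1-point table.
- **Both:** name the baseline used, after reconciling Protocol 9 (value before double-blind dosing for subjects randomized to ziprasidone) with SAP 3.4 (final double-blind visit for all non-ECG data).

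The cost is a few extra descriptive tables and matching wording in the two documents. The data are already collected and no new assessment is needed.
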